4.2.1.2.5 Serious Adverse Events

An event will be considered as a serious event if "Yes" is checked for "Serious" in the CRF.

SAEs will be analyzed using the following periods:

- Within 28 days after vaccination
- During the study (i.e., all SAEs occurred during the study)

4.2.1.2.6 Adverse Events of Special Interest

An event will be considered as an AESI if "Yes' is checked for "Is the event an AESI?" in the CRF.

AESIs will be analyzed using the same time periods as SAEs described in Section 4.2.1.2.5:

- Within 28 days after vaccination
- During the study (i.e., all AESIs occurred during the study)

4.2.2 Other Safety Endpoints

4.2.2.1 Pregnancy

This information will not be included in the analysis but will be listed separately. No derivation or imputation will be done.

4.2.2.2 Action Taken

This information will be summarized as collected, including missing observations. No derivation or imputation will be done.

4.2.2.3 Seriousness

This information will be summarized as collected. No derivation or imputation will be done.

4.2.2.4 Outcome

This information will be summarized as collected. No derivation or imputation will be done.

4.2.2.5 Causal Relationship

This information will be summarized as collected in the field "Relationship to study vaccine". Missing causal relationship will be handled as described in Section 3.4.3.1.2. Relationship to study procedure is only presented in the listing.

4.2.2.6 Adverse Events Leading to Study Discontinuation

This information will be summarized as collected. A flag is available in the clinical database for all AEs in order to identify AEs leading to discontinuation before the end of active phase.

In general, the items that are counted are:

- For participants disposition: if participants did not complete the study due to AE as recorded in Completion at End of Study form
- For safety overview: if participants did not complete the study due to AE as recorded in Completion at End of Study form or had any solicited or unsolicited AEs causing study discontinuation / termination as recorded in solicited reaction or unsolicited AE forms within the time period indicated
- For summary of unsolicited AEs by SOC / PT: A solicited AE that has "Caused Study Termination" checked that is at least Grade 1 or an unsolicited AE that has "Caused Study Termination" checked that is at least Grade 1 or missing and is within the time period indicated

4.2.3 Immunogenicity

4.2.3.1 Computed Values for Analysis

In order to appropriately manage extreme values (< LLOQ and \geq ULOQ) for analysis purposes, the following computational rule is applied to the values provided in the clinical database for each blood sample (BL) drawn:

- If a value is < LLOQ, then use the computed value LLOQ/2
- If a value is between \geq LLOQ and < ULOQ, then use the value
- If a value is \geq ULOQ, then use the computed value ULOQ

4.2.3.2 Fold-rise

The derived endpoint fold-rise is driven by both baseline and post-baseline computed values

as described in Section 4.2.3.1 and is computed as follows:

• Calculate the fold-rise of values as the ratio of post-baseline computed value divided by baseline computed value

For HAI assay, if the computed value is \geq 4-fold rise, then the derived \geq 4-fold rise indicator will be "Yes" for that test, otherwise \geq 4-fold rise will be "No".

Note: If baseline or post-baseline is missing, then the fold-rise is missing.

4.2.3.3 Seroconversion

Seroconversion is defined for HAI assay as either computed titer value < 10 (1/dilution [1/dil]) at D01 and post-injection computed titer value ≥ 40 (1/dil) at D29, or computed titer value ≥ 10 (1/dil) at D01 and a ≥ 4 -fold increase in computed titer value (1/dil) at D29.

4.2.4 Derived Other Variables

4.2.4.1 Age for Demographics

The calendar age will be used for demographics summary and age subgroups definition and will be analyzed as collected in CRF.

The age group of a participant in the study will be based on the calendar age as follows:

- "18 to 49 years" means from the day of their 18th birthday to the day before their 50th birthday
- " \geq 50 years" means from the day of the participant's 50th birthday

4.2.4.2 Duration of a Participant in the Trial

The duration of a participant's participation in the study is computed as follows:

• Maximum (Visit dates, Termination date, Follow-up date) – D01 date + 1.

4.2.4.3 Duration of the Study

The duration of the study is computed in days as follows:

Maximum of all participants (Visit dates, Termination date, Follow-up date) - minimum of all participants (D01 date) +1

4.2.4.4 Duration of a Participant in the Active Phase

The duration of a participant's participation in the active phase is computed as follows:

• Maximum (D29 date, Termination date) – D01 date + 1.

4.2.4.5 Duration of the Active Phase

The duration of the active phase is computed in days as follows:

Maximum of all participants (D29 dates, Termination dates) - minimum of all participants (D01 date) +1

5 Changes in the Conduct of the Trial or Planned Analyses

Not applicable.

6 Supporting Documentation

6.1 Appendix 1 List of Abbreviations

Ab	Antibody
AE	Adverse Events
AESI	Adverse events of special interest
AR	Adverse reactions
BL	Blood sampling
CRF	Case report form
D	Day
DC	diary card
DMC	Data Monitoring Committee
FAS	Full analysis set
GM	Geometric mean
GMT	Geometric mean of titer
GMTR	Geometric mean of titer ratio
GMFR	Geometric mean fold-rise
HAI	Hemagglutinin inhibition
IM	intramuscular
IIV4	Quadrivalent-inactivated influenza vaccine
IRT	Interactive Response Technology
LLOQ	Lower level of quantitation
MCMC	Markov chain Monte Carlo
MedDRA	Medical Dictionary for Regulatory Activities
NA	Not applicable
PPAS	Per-protocol analysis set
RCDC	Reverse cumulative distribution curve
RIV4	Recombinant influenza vaccine, Quadrivalent
SAE	Serious adverse events
SafAS	Safety analysis set
SAP	Statistical analysis plan
SOC	(Primary) System organ class

РТ	Preferred term
TLF	Tables, listings and figures
ULOQ	Upper level of quantitation

6.2 Appendix 2 Bayesian approach

Calculation of the posterior probability of the GMT ratio being > 0.667

Based on Bayesian approach (3), we are going to calculate the posterior probability of the true GMT ratio for each strain between RIV4 and IIV4 to be higher than the commonly accepted non-inferiority margin (0.667), which is equivalent to true mean difference on the log_{10} scale > -0.176.

We assume that HAI log₁₀titer x_i for each strain for any group IIV4 or RIV4 follows normal distributions with known variance σ^2 . Considering the following sampling model for data from the two groups:

$$\begin{aligned} X_{i,1} = \mu + \delta + \epsilon_{i,1} \\ X_{i,2} = \mu - \delta + \epsilon_{i,2} \\ \{\epsilon_{i,j}\} \sim i. i. d. normal (0, \sigma^2) \end{aligned}$$

Using this parameterization where $\theta_1 = \mu + \delta$ and $\theta_2 = \mu - \delta$, representing group mean on the \log_{10} scale for each group. We see that δ represents half the population difference in means, as $(\theta_1 - \theta_2)/2 = \delta$, and μ represents the pooled average, as $(\theta_1 + \theta_2)/2 = \mu$. Assuming standard deviation of HAI \log_{10} titer is known and equal to the sample standard deviation for each strain. Sine σ is known, no prior is needed for it. Convenient conjugate prior distributions for the unknown parameters μ , δ are

$$p(\mu, \delta) = p(\mu) \times p(\delta)$$
$$\mu \sim normal(\mu_0, \gamma_0^2)$$
$$\delta \sim normal(\delta_0, \tau_0^2)$$

Then the full conditional distribution of μ and δ are as follows:

$$\{\mu | x_{i,1}, x_{i,2}, \delta, \sigma^2\} \sim normal(\mu_n, \gamma_n^2), \text{ where}$$
$$\mu_n = \gamma_n^2 \times [\mu_0 / \gamma_0^2 + \sum_{i=1}^{n_1} (x_{i,1} - \delta) / \sigma^2 + \sum_{i=1}^{n_2} (x_{i,2} + \delta) / \sigma^2]$$
$$\gamma_n^2 = [1 / \gamma_0^2 + (n_1 + n_2) / \sigma^2]^{-1}$$

$$\{\delta | x_{i,1}, x_{i,2}, \mu, \sigma^2\} \sim normal(\delta_n, \tau_n^2), \text{ where}$$

$$\delta_n = \tau_n^2 \times [\delta_0 / \tau_0^2 + \sum_{i=1}^{n_1} (x_{i,1} - \mu) / \sigma^2 - \sum_{i=1}^{n_2} (x_{i,2} - \mu) / \sigma^2]$$

$$\tau_n^2 = [1/\tau_0^2 + (n_1 + n_2) / \sigma^2]^{-1}$$

For the prior distribution of μ and δ , with reference to US studies (PSC12 and PSC16) we give prior settings as Appendix Table 1 shown. The priors on γ_0^2 and τ_0^2 tend to make these prior

Confidential/Proprietary Information Page 23 of 27 distributions reasonably diffuse (essentially non-informative on the log₁₀ scale). Given a hypothetical observed data with $\delta = 0, \mu = 2.5, \sigma = 0.65$, the prior distribution and marginal posterior distribution of δ is shown in Appendix Figure 1. It is shown that these priors are so vague that the likelihood (the data contribution) has a strong influence on the posterior distribution estimation.

[figure not shown]
Parameter	value
μ_0	2.0
γ_0^2	12
δ_0	- 0.176/2
$ au_0^2$	10 ²

Appendix Table 1: prior settings for unknown parameters

Therefore, based on the above prior distribution, we can then calculate the posterior probability Pr ($2\delta > -0.176$ |data). The Markov chain Monte Carlo (MCMC) procedure is utilized to obtain samples from the posterior distribution. SAS example code is provided below.

The statistical criterion for demonstrating success (posterior probability threshold) is not proposed due to the not powered sample size and the nature of the descriptive study. But the corresponding threshold might be proposed in the bridge report for descriptive evaluation purpose.

Appendix Figure 1: Prior and posterior distributions for δ given a hypothetical observed data with $\delta = 0, \mu = 2.5, \sigma = 0.65$

```
SAS example code for the posterior probability calculation:
data aa;
 set add.adis;
 if paramn=1 and avisitn=2; ***paramn: parameter index in ADaM adis. Sample code only focus
on one parameter;
                 ***avisitn=2 is used to filter the post-vaccination titers.
 avallog=log10(aval);
 keep usubjid param paramn trt01pn trt01p aval avallog;
run;
/*==
     /*get the poopled mean and SD from data */
proc summary data=aa;
 var avallog;
 output out= stats(drop= type freq ) mean=mu pool n=n std=SD;
run;
/*got the group mean difference between RIV4 and IIV4*/
ods listing close;
ods output statistics = stats diff;
proc ttest data=aa alpha=0.05 ci=equal;
 class trt01pn ;
 var avallog;
run;
ods listing;
/*set initial value to mu pool, del; set SD as a fixed value obtained from data*/
proc sql noprint;
 select mean/2 into: del from stats diff (where=(method="Pooled"));
 select mu pool into: mu pool from stats ;
 select sd into: sd from stats ;
quit;
%put &del. &mu pool. &sd.;
/*======Start MCMC procedures:=====*/
/*generate posterior samples for mu and del*/
proc mcmc data=aa outpost=postout seed=123 nmc=10000 thin=2 monitor=( parms ) statistics;
                                      *** Postsumint= summary statistics;
 ods select PostSumInt;
 parm mu pool &mu pool. del &del.;
/* specify parameters to estimate and assign initial values to them*/
 prior mu_pool ~ normal(mean=2, var=1); /*specify prior distributions for the parameter mu that
represents the pooled average */
 prior del ~ normal(mean=-0.088, var=100);
```

Confidential/Proprietary Information Page 25 of 27 /*enable different avallog to have different mean and variance, depending on their group indicator*/

```
if trt01pn = 1 then do;
mu = mu_pool + del;
end;
else do;
mu = mu_pool - del;
end;
s2=&sd. * &sd.; /*Assuming standard deviation of HAI log10 titer is known and equal to the
sample standard deviation*/
model avallog ~ normal(mu, var=s2);
run;
```

```
/*get the posterior probability of the GMT ratio being > 0.667, which is equivalent to mean
difference on the log10 scale > -0.176.*/
proc format;
value delfmt low- -0.088=" mean difference on the log10 scale <= -0.176"
        -0.088 <- high= ' mean difference on the log10 scale > -0.176';
```

run;

```
ods output OneWayFreqs=stat1;
proc freq data = postout;
tables del /nocum;
format del delfmt.;
run;
```

7 References

- 1. Newcombe RG. Two-sided confidence intervals for the single proportion: comparison of seven methods. Stat Med. 1998;17(8):857-72.
- 2. Newcombe RG. Interval estimation for the difference between independent proportions: comparison of eleven methods. Stat Med. 1998;17(8):873-90.
- 3. Hoff PD. A First Course in Bayesian Statistical Methods. Springer-Verlag, New York, Springer Texts in Statistics, 2009.

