9.4 Statistical Analyses

The SAP will be finalized prior to database lock and it will include a more technical and detailed description of the statistical analyses described in this section. This section is a summary of the planned statistical analyses of the most important endpoints.

The endpoints for immunogenicity and safety are shown in Table 3.1.

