3.1 Statistical Hypotheses

No hypotheses will be tested. All analyses will be descriptive.

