3.4.2.1 Immunogenicity

The analysis of Hemagglutinin inhibition (HAI) Ab response measured at D01 and D29 will be performed by age subgroup, intervention group and pooled age group, including but will not be limited to:

- Geometric mean of HAI Ab titer (GMT) and 95% CI at D01 and D29
- Geometric mean fold-rise (GMFR) of HAI Ab titer and its 95%CI. Fold-rise is computed as individual titer ratio of post-vaccination value divided by baseline value.
- Number and percentage of participants with seroconversion (seroconversion rate): titer < 10 (1/dilution [1/dil]) at D01 and post-injection titer ≥ 40 (1/dil) at D29, or titer ≥ 10 (1/dil) at D01 and a ≥ 4-fold increase in titer (1/dil) at D29
- Number and percentage of participants with titer ≥ 40 (1/dil) at D01 and D29
- Number and percentage of participants with detectable titer ≥ 10 (1/dil) at D01 and D29

The 95% CIs for the GMTs and GMFR will be calculated using a normal approximation of log_{10} -transformed titers. The 95% CIs for the proportions will be based on the Clopper-Pearson method (1).

The ratios of GMTs (RIV4/IIV4) in each age group and pooled age group will be obtained between groups with the 95% CIs calculated using a normal approximation of log₁₀-transformed titers. The differences in the seroconversion rates between groups in each age group and pooled age group will be computed along with the 2-sided 95% CIs by the Wilson-Score method without continuity correction (2).

Reverse cumulative distribution curves in each age group and pooled age group against each strain will be performed for baseline (D01) and post-vaccination immunogenicity (D29).

The primary immunogenicity analyses will be performed on the Per-Protocol Analysis Set (PPAS) and on the Full Analysis Set (FAS). Details of both analyses sets are described in Section 3.3.

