3.4.2.3 Complementary analysis

In addition, as a complementary analysis to support bridging discussion, Bayesian method will be used to evaluate the probability of non-inferiority in terms of GMTs for post-vaccination HAI Ab titer. The posterior probability of the true ratio of GMTs (RIV4/IIV4) to be higher than the commonly accepted non-inferiority margin (0.667) will be calculated using the Bayesian approach to support bridging with previous non-inferiority trials.

Further details about the statistical methodology are provided in the Appendix 2.

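### Does leaving the posterior-probability threshold to the bridging report, with no date for fixing it, undermine the Bayesian non-inferiority analysis?

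*SAP*

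**What the plan says.** SAP 3.4.2.3 introduces the Bayesian calculation in a supporting role: "as a complementary analysis to support bridging discussion, Bayesian method will be used to evaluate the probability of non-inferiority". Appendix 2 defines the target as a true GMT ratio "higher than the commonly accepted non-inferiority margin (0.667), which is equivalent to true mean difference on the log_{10} scale > -0.176". It fixes the sampling model and the priors and gives example SAS code.

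On a success criterion, Appendix 2 states: "The statistical criterion for demonstrating success (posterior probability threshold) is not proposed due to the not powered sample size", and it also cites the descriptive nature of the study. The next sentence leaves a door open: "But the corresponding threshold might be proposed in the bridge report for descriptive evaluation purpose". The bridging report is not described anywhere else in the two documents.

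Three other statements set the context:
- SAP 3.1: "No hypotheses will be tested. All analyses will be descriptive".
- SAP 3.4.2.1: "The ratios of GMTs (RIV4/IIV4) in each age group and pooled age group will be obtained between groups with the 95% CIs". The same section runs the primary immunogenicity analyses on both the PPAS and the FAS.
- Protocol 9.4: "The SAP will be finalized prior to database lock and it will include a more technical and detailed description of the statistical analyses".

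**The concern.** The SAP first declines a criterion for success and then lets a threshold reappear in another document. Protocol 9.4 requires the SAP to be final before database lock. No matching rule covers the bridging report, and nothing says who sets the threshold, at what value or when. Read strictly, the sponsor could see the posterior probabilities and then choose a cut-off that they clear.

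This would matter if the cut-off became a verdict. The stated purpose is to link this trial to earlier non-inferiority trials, and a threshold turns a continuous probability into pass or fail. At this sample size, plausible results lie where the choice of cut-off decides the label. A claim of non-inferiority made that way would have no interpretable error rate.

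**Working it through.** **Inputs.** SD of log10 titre 0.65 and 71 evaluable participants per age-by-vaccine group (SAP 3.2); margin −0.176 on the log10 scale (SAP Appendix 2); prior on δ, half the mean difference, normal with mean −0.088 and variance 100 (Appendix Table 1 and code). The documents give no threshold, so 0.80, 0.90, 0.95 and 0.975 below are assumptions.

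**The plan's own figures.** 75 × 0.95 = 71.25, hence 71. The standard error of a difference in means is 0.65 × √(2/71) = 0.1091. Multiplied by the t quantile on 140 degrees of freedom (1.977) it gives 0.2157; the SAP states 0.216. For a single mean, 1.994 × 0.65/√71 = 0.1539; the SAP states 0.154. Both reproduce.

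**Posterior at an observed ratio of 1.00.** With equal arms, the posterior precision of δ is 1/100 + 2 × 71/0.65² = 0.01 + 336.10, so the prior carries almost no weight. The posterior SD of 2δ is 0.1091. The probability is Φ(0.176/0.1091) = Φ(1.613) = 0.947. A flat prior gives the same value to four decimals, and one minus the one-sided t-test p-value is 0.9455. The 95% CI for the ratio is 10^(±0.2157), or 0.61 to 1.64. Observed ratios of 0.8, 0.9 and 1.1 give 0.766, 0.884 and 0.977.

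**Effect of an assumed threshold T, one strain.** The observed ratio needed is 10^(−0.176 + z_T × SE). The chance of passing is Φ((log10 true ratio + 0.176)/SE − z_T). For pooled ages, 142 per arm, SE = 0.65 × √(2/142) = 0.0771; using SD 0.65 there is a further assumption.

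| T | Ratio needed, 71 per arm | Pass if true ratio 0.667 | Pass if true ratio 1, 71 per arm | Ratio needed, 142 per arm | Pass if true ratio 1, 142 per arm |
|---|---|---|---|---|---|
| 0.80 | 0.824 | 20% | 78.0% | 0.774 | 92.5% |
| 0.90 | 0.920 | 10% | 63.0% | 0.837 | 84.1% |
| 0.95 | 1.008 | 5% | 48.7% | 0.893 | 73.8% |
| 0.975 | 1.091 | 2.5% | 36.4% | 0.944 | 62.6% |

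With equal vaccines, moving T from 0.80 to 0.975 changes the label in 78.0 − 36.4 = 41.6% of cases in one age group and 92.5 − 62.6 = 29.9% with ages pooled. These figures depend on the SD. Over an assumed range of 0.4 to 0.8 (71 per arm, true ratio 1), the pass rate runs from 96.2% to 68.1% at T = 0.80 and from 74.6% to 25.8% at T = 0.975.

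**What the table shows.** The third column is simply one minus T, as it must be under a nearly flat prior. Any statistic cut at a threshold behaves in this way. T does not enter the model, the priors, the posterior probability, the GMT ratio or its CI. Following the SAP as written gives the same reported numbers for every value of T, including none.

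**Are the age grouping and analysis set also open?** The example code selects on "if paramn=1 and avisitn=2" and on nothing else. But it is labelled as sample code for a single parameter, and the general rules supply the rest. Protocol 9.4.1 calls for results by age group and overall, and SAP 3.4.1 for results by age group and vaccine group. SAP 3.4.2.1 gives the GMT ratio for each age group and pooled, with the immunogenicity analyses on the PPAS and the FAS. An analyst reading these together would report the posterior probability in the same layout.

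**The case for a change.** The best case for a change is that the later threshold refers back to the criterion for demonstrating success, so calling it descriptive does not alter what it is. The reasons given for setting none, an unpowered sample and a descriptive study, apply equally in the bridging report. Adding a sentence before database lock would cost almost nothing and remove the doubt.

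Much of this stands. The documents do not date the threshold, and one chosen after sight of the results could not support a claim of non-inferiority. At 71 per arm the label would often turn on it.

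The step to a needed change is weaker. The text permits a late choice; it does not plan one. It speaks only of a possible proposal, for descriptive evaluation, and no passage attaches a success statement to it. The Protocol 9.4 rule on finalising the SAP covers the analyses described in the protocol. Protocol 9.4.2 asks for the posterior probability to be calculated, and Appendix 2 specifies that calculation. A threshold for a separate report is not an analysis that the SAP was bound to contain. Having this SAP forbid any threshold in that report would be a preference that the sponsor could reasonably dispute.

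**Conclusion.** No change to the plan is called for. The gap is real but small: an optional reference threshold, in a report that these documents do not otherwise describe, has no stated date. It alters no estimate, interval or posterior probability and breaks no promised error rate. The posterior is close to a restatement of the planned GMT ratio and CI (0.9467 against 0.9455 from the t-test at a ratio of 1.00), so readers can judge any cut-off for themselves.

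The figures rest on SD 0.65, 71 per arm (142 pooled) and thresholds that are assumed. The conclusion rests on the analysis staying descriptive, as SAP 3.1 says. If the bridging report were to call a strain non-inferior because it cleared a threshold, that report would need to say when the threshold was chosen, and one set after unblinding should be read as post hoc. That is a test for the bridging report, not a fault in this SAP.

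### Minor: the Appendix 2 example code fixes σ at the total SD, where the model equations imply the within-vaccine SD, and the pooled-age GMT ratios leave out the age group used in randomisation

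*SAP*

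**What the plan says.** SAP Appendix 2 models one group as μ + δ plus error and the other as μ − δ plus error, with independent normal errors of variance σ². It says the log10 titre "for any group IIV4 or RIV4 follows normal distributions with known variance". It then fixes σ: the SD "is known and equal to the sample standard deviation for each strain". Nothing states whether that SD is taken within vaccine groups or across both.

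The example code makes the choice. Under the comment "get the poopled mean and SD from data", PROC SUMMARY runs on the log10 titres with no CLASS or BY statement, so its SD is around the grand mean of both vaccines. The line "select sd into: sd from stats" carries it forward, and its square is the fixed likelihood variance in PROC MCMC. PROC TTEST is also run by vaccine, but only half the mean difference is kept from its Pooled row, as a starting value for δ. The sampler setting is "seed=123 nmc=10000 thin=2", which keeps 5,000 draws.

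The role of this step is limited. SAP 3.4.2.3 describes it "as a complementary analysis to support bridging discussion", and Appendix 2 adds: "The statistical criterion for demonstrating success (posterior probability threshold) is not proposed". It does allow that a threshold may be suggested later, in the bridge report.

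On age: SAP Section 1 randomises 1:1 within each age group. SAP 3.4.2.1 plans the GMT ratio in each age group and for pooled ages. Protocol 9.4.1 provides all analyses by age group and overall. Neither the pooled ratio nor the Appendix 2 mean contains age group, and the printed data step has no age filter.

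**The concern.** If σ is the SD around each vaccine's own mean, the SD around the grand mean is a different quantity: it also contains the observed RIV4–IIV4 difference. That difference would then enter twice, once through δ and once through the error variance. A programmer working from the equations and one working from the code would get different posterior probabilities for the figure meant to support bridging.

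The age question concerns precision. When allocation is balanced within age groups and titres differ by age, leaving age out of a pooled comparison puts between-age variation into the error term. The interval is then wider than it needs to be.

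**Working it through.** **Inputs.** SD of log10 titre 0.65 and 71 evaluable per age-by-vaccine cell (SAP 3.2); prior for δ normal with mean −0.088 and variance 100, and margin 0.667, or −0.176 on the log10 scale (Appendix 2). The observed ratio is not given, so a range is shown. I take 0.65 as the within-group SD.

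**The plan's own figures.** Half-width for one mean: t(0.975, 70) × 0.65/√71 = 0.1539. For a difference: t(0.975, 140) × 0.65 × √(2/71) = 0.2157. Both match SAP 3.2 (0.154 and 0.216).

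**Coded σ, one age group.** With N = 142 and d = log10(observed ratio):

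total SD² = [(N − 2) × 0.65² + N × (d/2)²] / (N − 1)

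This equals 0.65² when N(d/2)² = 0.65², that is |d| = 2 × 0.65/√142 = 0.109, or ratios of 0.778 and 1.286. Between those values the coded σ is slightly too small, because the divisor N − 1 outweighs the added term. Outside them it is slightly too large.

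**Posterior.** With equal arms, δ given the data is normal with precision 1/100 + N/σ² and mean [−0.088/100 + N(d/2)/σ²] divided by that precision. Pr(δ > −0.088) is then:

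| Observed ratio | Coded σ | Pr, coded σ | Pr, σ = 0.65 |
|---|---|---|---|
| 0.46 | 0.6694 | 0.0756 | 0.0697 |
| 0.50 | 0.6651 | 0.1313 | 0.1259 |
| 0.667 | 0.6537 | 0.5005 | 0.5005 |
| 0.75 | 0.6507 | 0.6799 | 0.6801 |
| 0.85 | 0.6487 | 0.8336 | 0.8331 |
| 1.00 | 0.6477 | 0.9473 | 0.9467 |
| 1.50 | 0.6537 | 0.9993 | 0.9994 |

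Over ratios from 0.2 to 3, the largest shift below the margin is +0.006, near 0.46. Above the margin, shifts lie between −0.0003 and +0.0007. If the SD were 0.40, 0.50 or 0.80, the largest shift below the margin would be 0.011, 0.008 or 0.005; above the margin it stays within 0.0022. With ages pooled (142 per arm) and no age gap, the largest shift at SD 0.65 is 0.0046.

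**Simulation error.** √[p(1 − p)/5000], treating draws as independent: 0.003 at p = 0.95, 0.005 at p = 0.13.

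**Pooled ages.** N = 284 in four cells of 71, within-cell SD 0.65 on N − 4 df, and G = log10 of an assumed fold gap between age groups in D29 GMT:

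within-arm SD² = [(N − 4) × 0.65² + N × (G/2)²] / (N − 2)

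| Assumed age gap | Within-arm SD | Against 0.65 |
|---|---|---|
| none | 0.6477 | −0.4% |
| 1.5-fold | 0.6537 | +0.6% |
| 2-fold | 0.6651 | +2.3% |
| 3-fold | 0.6905 | +6.2% |

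The log-scale interval width changes in the same proportion.

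Correcting σ alone does not remove this. At a 3-fold gap and an observed ratio of 0.55, the posterior probability is 0.158 as coded, 0.154 with the pooled within-vaccine SD, and 0.139 with an age term. At a ratio of 0.80 the three values are 0.833, 0.833 and 0.847.

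**The case against.** The code can be defended as following the text. The sentence that fixes σ asks for a sample SD per strain, not per vaccine, and the code says openly that it takes one SD from the data. Only the equations point to a within-group σ. That stands: this is an ambiguity in the text, settled in the code by a near-equivalent value. It is not an analysis that departs from an explicit instruction.

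It is also fair that the code is illustrative (it handles one parameter and has no age or analysis-set filter), that the analysis is complementary, and that no threshold is set. A shift of this size could matter only to a result lying almost exactly on a threshold chosen later.

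On age, a reader might infer that Appendix 2 leaves open whether pooled ages are analysed. Protocol 9.4.1 answers that with its general rule. A reader might also infer that the pooled ratio is confounded by age. With 1:1 allocation inside each age group it is not. What remains is precision, and the gain depends on an age gap that the documents do not give.

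**Conclusion.** Both points hold as minor ones.

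First, the equations and the example code use different SDs, and the sentence between them does not settle which is meant. At the planning values the posterior probability changes by at most about 0.006, and by under 0.001 above the margin. A reader might infer that the code inflates the error term throughout, or that the bridging probability is unreliable. Neither is supported: for observed ratios of about 0.78 to 1.29 the coded σ is slightly too small, and the change everywhere is about the size of simulation error. The reason to act is that text and code should agree before the figure is used in the bridging discussion.

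Second, analysing pooled ages with the factor used in randomisation is a free gain in precision and not the repair of an error. It is worth about 0.6% to 6.2% of log-scale interval width under the assumed 1.5- to 3-fold gaps, against 0.4% the other way if there is no gap.

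These sizes rest on SD 0.65, 71 per cell and, for the second point, the assumed gaps.

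**What to change.** 1. In the PROC SQL step, read the SD from the Pooled row of the existing PROC TTEST output instead of the PROC SUMMARY output. In the Appendix 2 text, say that σ is the pooled within-vaccine-group SD for the strain. Cost: one line of example code and one clause.

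2. For pooled-age results, compute the GMT ratio and its CI in SAP 3.4.2.1 from a model of log10 titre with vaccine and age group. In the pooled-age Bayesian run, add age group to the MCMC mean and set σ to that model's residual SD. Cost: one model term and one sentence.

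Neither change affects trial conduct or data collection.
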